2.3 Global Good/Intellectual Ventures Pediatric Mask (Nasal Reservoir Cannula)

Improving oxygen delivery and extending oxygen supplies to ill patients with respiratory distress can reduce fatalities in resource-poor settings. Global Good has developed a low cost oxygen mask (nasal reservoir cannula) to more efficiently deliver oxygen to the pediatric patient by increasing dead space to recapture a portion of expelled oxygen using

¹ Efficiency gain is based on adult patients. Most conserving devices are not approved for pediatric use.

[figure not shown]
the spatial distribution of the nasal reservoir cannula volume and length of surface seal. This nasal reservoir cannula fits over a standard nasal cannula (also termed prong) (see Fig. 1 below). The system is designed to reduce administered oxygen to deliver an equal or higher fraction of inspired oxygen (FiO₂) per oxygen delivered (L/min) compared with a standard nasal cannula alone. Please refer to the device brochure (Appendix I) for instructional details on the nasal reservoir cannula.

Figure 1. Novel Nasal Reservoir Cannula

[figure not shown]
Mask performance was evaluated using a breathing simulator developed at the Global Good Laboratory (Bellevue, WA). The system consists of a breathing simulator (ASL 5000, IngMar Medical, Pittsburgh, PA) paired with an anatomically correct airway and face constructed by 3D printing computerized tomography scan data (Fig. 2). Carbon dioxide was titrated into the lung to simulate metabolism. The end-tidal carbon dioxide (CO₂), which is equivalent to the maximal concentration of carbon dioxide at the end of an exhaled breath, and FiO₂ were measured. An array of breathing waveforms was tested to bound mask performance.

Figure 2. Pediatric Breathing Simulator

For hospitalized patients with hypoxic respiratory illnesses, the minimal oxygen delivered recommended by the World Health Organization (WHO) is in ranges typically used in low-flow nasal cannulas; in vitro experiments on the breathing simulator indicate that the novel nasal reservoir cannula may be able to provide the same or higher FiO₂ at approximately 2.5-times lower oxygen flow rate (L/min) compared with a standard nasal cannula alone (Global Good, data on file; see Fig. 3). This can result in less oxygen used than conventional delivery systems, which may be valuable for resource limited settings where oxygen supplies are limited.

Figure 3 Oxygen Flow and FiO₂ of Novel Mask (Nasal Reservoir Cannula)

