8.1.3 Serious Adverse Event Definition and Reporting Procedures

For purposes of this trial, a serious adverse event (SAE) is defined as an AE that suggests a significant hazard or side effect, regardless of the relationship to study treatment. An SAE includes, but may not be limited to, any event that:

- Results in death.
- Is life-threatening. This definition implies that the subject, in the view of the investigator, is at immediate risk of death from the event. It does not include an event that, had it occurred in a more serious form, might have caused death.
- Requires inpatient hospitalization or prolongs existing hospitalization.
- Results in persistent or significant disability/incapacity.

Any SAE that meets the above definition and occurs in a subject during the course of the study must be reported to the sponsor by telephone within 24 hours of the investigator becoming aware of the event. In addition, a SAE reporting form must be completed by the investigator and faxed to the study sponsor within 24 hours of the investigator becoming aware of the event. In addition, the site investigator must report SAEs to their local Institutional Review Board/Institutional Ethics Committee (IRB/IEC) in accordance with the IRB/IEC's standard operating procedures and policies.

Medical and scientific judgment will be exercised in deciding whether classification of an adverse event as serious is appropriate in other situations, such as important medical events that may not be immediately life-threatening or result in death or hospitalization, but may jeopardize the subject or require intervention to prevent one of the outcomes listed in the definition above. These should also usually be considered serious. Examples of such events include allergic bronchospasm requiring intensive treatment in an emergency room or at home, blood dyscrasias or convulsions that do not result in inpatient hospitalization, or the development of drug dependence or abuse.

Please refer to the Data and Safety Monitoring Plan (Appendix H) for further details, including stopping rules.

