8.1.4 Laboratory Tests

Clinical laboratory tests will be performed at the times specified in the Study Schedule (see Appendix A) and will follow the local and regular protocol for patients with respiratory distress. All clinical laboratory assessments will be analyzed at the participating site's local laboratory. Clinically significant laboratory abnormalities (see Appendix F), which

are new or worsen during the study period, will be reported as AEs or SAEs as appropriate based on the above definitions.

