Appendix F: Serious Adverse Event Reporting Form

Nasa	ocol Title: A Feasibility Study Evaluating a Novel Mask (Nasal Reservoir Cannula) Plus Standard al Cannula vs Standard Nasal Cannula Alone for Supplemental Oxygen Delivery in the Treatment of pitalized Pediatric Patients with Hypoxemia Due to Severe Pneumonia
	Pt_IP number: Study ID number:
1.	SAE Onset Date: (dd/mm/yyyy)
2.	SAE Stop Date:(dd/mm/yyyy)
3.	Location of serious adverse event:
4.	Was this an unexpected adverse event? Yes No
5.	Brief description of participant(s) with no personal identifiers: Sex: F M Age:
6.	Brief description of the nature of the serious adverse event (attach description if more space needed):
7.	Category of the serious adverse event:
	☐ death – date//(dd/mmm/yyyy) ☐ congenital anomaly / birth defect ☐ life-threatening ☐ required intervention to prevent ☐ hospitalization-initial or prolonged permanent impairment ☐ disability / incapacity ☐ other:
8.	Intervention type:
	Medication or Nutritional Supplement: specify
	Device: Specify:
	Surgery: Specify:
	Behavioral/Life Style: Specify:

9.	Relationship of event to intervention:
	Unrelated (clearly not related to the intervention) Possible (may be related to intervention) Definite (clearly related to intervention)
10.	Was study intervention discontinued due to event? Yes No
11.	What medications or other steps were taken to treat serious adverse event?
12.	List any relevant tests, laboratory data, history, including preexisting medical conditions
13.	Type of report:
	☐ Initial ☐ Follow-up ☐ Final
	Signature of Principal Investigator: Date:

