This study involves a newly developed non-invasive investigational device, a nasal reservoir cannula that can significantly improve access to effective and safe oxygen therapy for children with respiratory distress. This device is an add on approach to be used in conjunction with a standard nasal cannula with prongs which will allow a more rational use of oxygen and in turn better adjustment of treatment to patient needs. The device does not replace the standard method of care of oxygen delivery via nasal cannula; therefore, it does not present any new or additional potential for serious risk to health, safety or welfare of subjects.

Potential risks might be that the subject develops a condition or begins a therapy that would have excluded entry into the study such as hypercapnia, requiring intubation or non-invasive or invasive positive—pressure ventilation, or suspected or known pneumothorax. It is important to note that these potential risks are independent of the investigational device

and might be a potential risk during any type of oxygen therapy. The study investigators have years of experience providing clinical care for children with respiratory problems and conducting clinical research in children.

5. SAE Reporting- SAEs that are unanticipated, serious (grades 3 and 4), and/or possibly related to the study intervention must be reported to the sponsor by telephone within 24 hours of the investigator becoming aware of the event. In addition, a SAE reporting form must be completed by the site PI and faxed to the sponsor within 24 hours of the PI becoming aware of the event. In addition, the site PI must report SAEs to the Mulago Research and Ethics Committee (MREC) in accordance with the MREC's standard operating procedures and policies. Anticipated SAEs or those unrelated to the study intervention will be reported to the same individuals/entities in accordance with requirements.

Sponsor phone numbers include: [name]: [name] or [name] [name] (United States-based).

Investigator phone numbers include: [name] [name] (Uganda-based.

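### Appendix H calls hypercapnia independent of a device that works by adding dead space, and its SAE timing rule and laboratory cross-reference conflict with or fail the main protocol

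*Protocol*

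**What the plan says.** **Mechanism and monitoring.** Section 2.3 describes a reservoir that delivers oxygen more efficiently "by increasing dead space to recapture a portion of expelled oxygen". Sections 4.1 and 10.3 make transdermal CO2 and capillary blood gases safety measures. Section 4.2.2 has CO2 recorded every 15 minutes and a blood gas taken at the end of each period.

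**Risk statement.** Appendix H, B.4 reasons that the device is added to the standard cannula rather than replacing it, so "it does not present any new or additional potential for serious risk to health, safety or welfare of subjects". It then allows that a child might develop "a condition or begins a therapy that would have excluded entry into the study such as hypercapnia", and adds: "It is important to note that these potential risks are independent of the investigational device".

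**SAE timing.** Section 8.1.3 sets a 24-hour limit for all SAEs: "Any SAE that meets the above definition and occurs in a subject during the course of the study must be reported to the sponsor". Its SAE definition applies whatever the relationship to treatment. Appendix H, B.5 attaches the same limit to a narrower set: "SAEs that are unanticipated, serious (grades 3 and 4), and/or possibly related to the study intervention must be reported to the sponsor by telephone". A later sentence in B.5 covers SAEs that are anticipated or unrelated. They go to the same recipients as requirements dictate, with no time stated.

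**Laboratory values.** Section 8.1.4 opens its rule with "Clinically significant laboratory abnormalities (see Appendix F), which" and makes new or worsening abnormalities reportable as AEs or SAEs. Appendix H repeats the pointer. The appendix it names is headed "Appendix F: Serious Adverse Event Reporting Form".

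**The concern.** The study is meant to inform later trials of the device's safety, yet Appendix H answers one safety question in advance. The trial is open-label and causality is the investigator's judgment (Section 8.1.2; Appendix H, B.3). An assessor who has read that hypercapnia cannot come from the device may weigh a CO2 rise on the mask differently. Treatment-related AEs are tabulated separately (Section 10.5.6), and the report after 10 patients asks whether AE rates match what was assumed beforehand (Appendix H, D).

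The SAE conflict affects sponsor oversight. Section 8.1.3 sends the reader to Appendix H for further detail, so site staff may well follow the narrower text. The laboratory pointer leaves staff without the criterion they are told to look up.

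**Working it through.** The protocol gives no figure on this point to reproduce, so the check is mainly a comparison of sections.

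1. **Mechanism against risk statement.** Section 2.3 attributes the effect to added dead space and reports that the bench simulator fed CO2 into the lung and measured end-tidal CO2. The device brochure (Appendix I) limits use to settings with pulse oximetry and blood gas analysis. B.4's argument is that an add-on brings no new serious risk. It does not follow, because the added part is what creates the dead space.

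2. **Is the volume negligible?** Inputs are the mask volumes and weight bands in Section 4.1. Volume divided by weight gives 30/8 = 3.75, 30/13 = 2.31, 50/14 = 3.57 and 50/26 = 1.92 mL/kg. The protocol states no tidal volume. Assuming 5 to 10 mL/kg, the nominal volume runs from 1.92/10 = 19% to 3.75/5 = 75% of a breath. Oxygen inflow and the loose fit reduce the effective dead space, so this is an upper bound. It shows that the mechanism cannot be dismissed on size; it does not show CO2 retention.

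3. **Attribution scale.** B.3 has four grades and none for unlikely. The lowest, unrelated, requires certainty. The next, possibly, asks for a response pattern already known or expected, and B.4 denies any such pattern for hypercapnia. The two parts of the appendix pull in opposite directions.

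4. **SAE timing, case by case**, for a grade 3-4 SAE:

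| SAE | Section 8.1.3 | B.5, any one condition suffices | B.5, all conditions needed |
|---|---|---|---|
| Anticipated, unrelated | 24 h | 24 h by its first sentence, no limit by its last | no limit |
| Anticipated, possibly related | 24 h | same conflict | no limit |
| Unanticipated, unrelated | 24 h | same conflict | no limit |
| Unanticipated, possibly related | 24 h | 24 h | 24 h |

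The two sections agree without qualification only in the last row. Serious hypercapnia could be placed in any of the four. B.4 foresees it as a potential risk but does not list it among the expected ones, and calls it independent of the device.

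5. **Laboratory chain.** Section 8.1.4 and Appendix H both lead to Appendix F, which holds no laboratory criteria. Appendix G gives analyser reportable ranges (pCO2 5 to 130 mm Hg, pH 6.5 to 8.2). What remains is the site principal investigator's judgment of clinical significance (Appendix H). The entry limits in Section 6.1 (pCO2 above 55 mm Hg, pH below 7.20, lactate above 3 mmol/L) are defined on room air and are not linked to AE recording.

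6. **Why single events count.** The chance of at least one event is 1 − (1 − p)^n. For assumed true risks p of 5%, 10% and 20%, this is 40%, 65% and 89% with n = 10, and 64%, 88% and 99% with n = 20. At the lower of these risks the study may see only one or two events, so how each is classed and reported matters.

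**The case against.** A reader might infer that device-caused CO2 retention will be classed as unrelated, reported late, and lost from the safety conclusion. The protocol does not support that.

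- B.4 is a risk narrative; attribution follows B.3 and Section 8.1.2. Unrelated requires certainty, which a CO2 rise beginning on the mask would hardly meet. The scale also considers timing and the effect of stopping, and both can be seen across the two periods.
- AEs are recorded whatever their cause (Section 8.1.1), and all of them are tabulated, not only the related ones (Section 10.5.6). CO2 and blood gases are safety variables summarized by treatment group (Sections 10.3 and 10.5.1). Hypercapnia leads to withdrawal (Section 8.1.5), and withdrawals are listed with reasons (Section 10.5.3).
- Section 8.1.3 remains in force, and B.5 can be read so that grade 3 or 4 alone triggers the 24-hour report.

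It is also tempting to say that Appendix G would let a pCO2 of 56 to 130 mm Hg pass unflagged. That treats reportable ranges as normal ranges. Despite the appendix title, its tables are labelled as reportable ranges, and no AE rule cites them.

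All of this stands, and it limits the consequence. It does not remove the contradiction on mechanism, the two different SAE rules, or the wrong reference.

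**Conclusion.** Three faults in the text are established: the independence and no-added-risk statements conflict with the stated mechanism and the CO2 monitoring; Appendix H, B.5 is narrower than Section 8.1.3; and the laboratory rule points to a form. Confidence in these is high.

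The effect is a possible influence on attribution and an unreconciled reporting rule, not a demonstrated bias or an exemption for CO2 events. The documents make CO2 rebreathing plausible and do not show that it occurs. The 19% to 75% range depends on an assumed tidal volume and is an upper bound; the event probabilities depend on assumed risks. The reassurance from the tables and CO2 summaries assumes that treatment group there means the treatment in use, since every child receives both. On that footing this is a should-fix.

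**What to change.** 1. In Appendix H, B.4, delete the statements that the risks are independent of the device and that it adds no potential for serious risk. Acknowledge CO2 retention as a possible device-related risk, to be attributed case by case under the B.3 scale.
2. Make Appendix H, B.5 match Section 8.1.3, so that every SAE reaches the sponsor within 24 hours whatever its relationship or expectedness.
3. Correct the Appendix F reference in Section 8.1.4 and Appendix H. Reconcile Section 6.1, Section 8.1.4, Appendix G and Appendix H on what flags a laboratory value for AE recording. No threshold is proposed here.

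Three steps should be avoided. A compulsory rating of at least possibly related would replace case-by-case judgment. Labelling CO2 retention as anticipated while B.5 stands as written could take it out of the 24-hour rule. Carrying the entry limits over as AE flags would apply room-air criteria to children on oxygen.

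The cost is a wording amendment with ethics notification, and possibly a few more expedited reports. Treatment, assessments and sample size are unchanged.

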APPENDIX I DEVICE BROCHURE:

Global Good/ Intellectual Ventures Mask (Nasal Reservoir Cannula)

Rationale:

Used properly this oxygen conserving nasal reservoir cannula will provide the patient adequate oxygen support equal to that of with conventional nasal cannula with prongs and the following added benefits:

- It will take a lower oxygen flow rate (l/min) to provide the same level of oxygenation in the body, which can be as much as 50% less (depending on the actual flow rate) than that of with a standard nasal cannula
- In case of using an oxygen storage system (e.g. oxygen cylinder), it will last significantly longer and in turn increase treatment capacity, spare resources with the same level and quality of care

Directions:

The mask is recommended for patients aged ≥ 1 year and ≤ 6 years with body weight of ≥ 8 kg and ≤ 26 kg. The proper mask size should be selected based on the patient's body weight (see table 1). Patients with a body weight of 8-13 kg should receive treatment with the small 30 ml mask and patients with a body weight of 14-26 kg should receive treatment with the large 50 ml mask.

The duration of the treatment and the oxygen flow rate should be based on the clinical judgment of the physician. This mask should only be implemented when the patient is monitored by adequate pulse oximetry and blood gas analysis tools.

Table 1. Mask size selection should be made based on patient weight.

Mask size	Child weight
Small (30 mL)	8-13 kg
Large (50 mL)	14-26g

Application:

- 1. Connect the standard nasal cannula to the oxygen source.
- 2. Turn on the oxygen and set flow rate (l/min).
- 3. Insert the mask over the conventional nasal cannula with prongs by installing the prongs into the respective slots of the mask.
- 4. Place the mask over the nose of the patient. The nasal piece does not need to tightly cover the nose but should rest loosely on the nose and the philtrum (upper lip) of the patient with the prongs extending into the nostrils.
- 5. Place the nasal cannula flexible tubing over the ears of the patient and then under the chin (per manufacturer's instructions). Slide the bola of the standard nasal cannula up toward the chin.

Cleaning:

The mask is disposable and should be used on an individual basis. During the duration of the oxygen substitution treatment if the mask gets contaminated with body fluids or secretions of the patient it can be washed with a mild soap and warm water, and thereafter can be wiped and disinfected with 70% alcohol. After total evaporation of the alcohol the mask may be re-used on the same individual. The use of bleach may not be recommended since residual bleach may cause skin, eye or respiratory tract irritation.

Humidification:

The system may be used with conventional supplementary humidifiers attached via a standard nasal cannula.

APPENDIX J Blood draw limits and anticipated blood draw volumes

Blood draw limits by weight

Weight in kg	Limit for single blood draw (mL) *Calculated as 2 mL/kg	Limit for 24 hour period (mL) *Calculated as 3 mL/kg
8	16	24
9	18	27
10	20	30
11 - 15	22 - 30	33 - 45
16 - 20	32 - 40	48 - 60
21 - 25	42 - 50	63 - 75
26	52	78

Blood draw volumes for this study (all in mL)

Laboratory test	Screening	Period 1	Period 2
Capillary blood gas (CBG) with lactate	0.095	0.095	0.095
Complete blood count (CBC)	1		
Hemoglobin (Hb) rapid test	0.01		
Malaria rapid test	0.05		
Blood glucose (point of care)	0.05		
Metabolic panel ^a	3		
Total each period (range)	1.19 - 4.21	0.095	0.095
Total overall (range)	1.38 - 4.40		

a. Metabolic panel done *only* if obtained as part of standard care.
